9.5.3 Appropriateness of Measurements

All clinical assessments, including platelet counts, are standard measurements commonly used in studies of subjects with thrombocytopenia associated with liver disease.

The safety assessments to be performed in this study, including but not limited to hematology analyses, blood chemistry tests, urinalysis, physical examinations, ECGs, Doppler sonography, vital signs, and assessment of AEs, are standard evaluations to ensure subject safety.

9.5.4 Reporting of Serious Adverse Events, Pregnancy, and Other Events of Interest

9.5.4.1 Reporting of Serious Adverse Events

All SERIOUS ADVERSE EVENTS, regardless of their relationship to study treatment, must be reported on a completed SAE form by email or fax as soon as possible but no later than 24 hours from when the investigator becomes aware of the event.

Deaths and life-threatening events should be reported immediately by telephone. The immediate report should be followed up within 24 hours by emailing or faxing the completed SAE form.

Serious adverse events, regardless of causality assessment, must be collected through the last visit and for 30 days after the subject's last dose. All SAEs must be followed to resolution or, if resolution is unlikely, to stabilization. Any SAE judged by the investigator to be related to the study treatment should be reported to the sponsor regardless of the length of time that has passed since study completion.

The detailed contact information for reporting of SAEs is provided in the Investigator Study File.

For urgent safety issues, please ensure all appropriate medical care is administered to the subject and contact the appropriate study team member listed in the Investigator Study File.

It is very important that the SAE report form be filled out as completely as possible at the time of the initial report. This includes the investigator's assessment of causality.

Any follow-up information received on SAEs should be forwarded within 1 business day of its receipt. If the follow-up information changes the investigator's assessment of causality, this should also be noted on the follow-up SAE form.

Preliminary SAE reports should be followed as soon as possible by detailed descriptions including copies of hospital case reports, autopsy reports, and other documents requested by the sponsor.

The investigator must notify his/her IRB/IEC of the occurrence of the SAE, in writing, if required by their institution. A copy of this communication must be forwarded to the sponsor to be filed in the sponsor's Trial Master File.

9.5.4.2 Reporting of Pregnancy and Exposure to Study Drug Through Breastfeeding

Any pregnancy in which the estimated date of conception is either before the last visit or within 30 days of last study treatment, or any exposure to study drug through breastfeeding during study treatment or within 30 days of last study treatment, must be reported.

If an adverse outcome of a pregnancy is suspected to be related to study drug exposure, this should be reported regardless of the length of time that has passed since the exposure to study treatment.

A congenital anomaly, death during perinatal period, an induced abortion, or a spontaneous abortion are considered to be an SAE and should be reported in the same time frame and in the same format as all other SAEs (see Reporting of Serious Adverse Events [[Section 9.5.4.1](#)]).

Pregnancies or exposure to study drug through breastfeeding must be reported by fax or email as soon as possible but no later than 1 business day from the date the investigator becomes aware of the pregnancy. The contact information for the reporting of pregnancies and exposure to study drug through breastfeeding is provided in the Investigator Study File. The Pregnancy Report Form must be used for reporting. All pregnancies must be followed to outcome. The outcome of the pregnancy must be reported as soon as possible but no later than 1 business day from the date the investigator becomes aware of the outcome.

A subject who becomes pregnant must be withdrawn from the study.

9.5.4.3 Reporting of Other Events of Interest

REPORTING OF ADVERSE EVENTS ASSOCIATED WITH STUDY DRUG OVERDOSE, MISUSE, ABUSE, OR MEDICATION ERROR

Adverse events associated with study drug overdose, misuse, abuse, and medication error refer to AEs associated with uses of the study drug outside of that specified by the protocol. Overdose, misuse, abuse, and medication error are defined as follows:

Overdose	Accidental or intentional use of the study drug in an amount higher than the protocol-defined dose
Misuse	Intentional and inappropriate use of study drug not in accordance with the protocol
Abuse	Sporadic or persistent intentional excessive use of study drug accompanied by harmful physical or psychological effects
Medication error	Any unintentional event that causes or leads to inappropriate study drug use or subject harm while the study drug is in the control of site personnel or the subject.

All AEs associated with an overdose should be captured on the Adverse Event CRF. Adverse events associated with overdose, misuse, abuse, or medication error should be reported using the

procedures detailed in Reporting of Serious Adverse Events ([Section 9.5.4.1](#)) even if the AEs do not meet serious criteria. Abuse is always to be captured as an AE. If the AE associated with an overdose, misuse, abuse, or medication error does not meet serious criteria, it must still be reported using the SAE form and in an expedited manner but should be noted as nonserious on the SAE form and the Adverse Event CRF.

REPORTING OF SIGNIFICANT LABORATORY ABNORMALITY

Any significant treatment-emergent laboratory abnormality observed during the clinical study should be entered on the Adverse Event CRF and reported using the procedures detailed in Reporting of Serious Adverse Events ([Section 9.5.4.1](#)), even if the laboratory abnormality does not meet serious criteria. If the significant laboratory abnormality does not meet serious criteria, it must still be reported using the SAE form and in an expedited manner but should be noted as nonserious on the SAE form and the Adverse Event CRF.

A laboratory result should be considered a treatment-emergent significant abnormality if the result:

- Is within normal limits at baseline and has increased in severity to meet the sponsor's grading criteria for laboratory values of Grade 3 or above
- Is outside normal limits at baseline and increases in severity to the sponsor's grading criteria for laboratory values of Grade 4 or above. These abnormalities are automatically considered to be serious, with the exception of expected and reproducible hematologic abnormalities.
- Is otherwise considered by the investigator to meet serious criteria as defined in [Section 9.5.1.5](#) (Serious Adverse Events and Other Events of Interest)

Significant laboratory abnormalities should not be listed as separate AEs or SAEs if they are considered to be part of the clinical syndrome that is being reported as an AE or SAE.

REPORTING OF STUDY-SPECIFIC EVENTS

Study-specific events (ie, recurrence of thrombocytopenia [defined as a platelet count of $<10 \times 10^9/L$ and $10 \times 10^9/L$ less than baseline count within 30 days of discontinuation]); thromboembolic events; bleeding events (WHO Grade 2 to 4); and platelet transfusion-related complications should be entered on the Adverse Event CRF and reported using the procedures detailed in Reporting of Serious Adverse Events ([Section 9.5.4.1](#)), even if the study-specific event does not meet serious criteria. If the event does not meet serious criteria, it must still be reported using the SAE form and in an expedited manner but should be noted as nonserious on the SAE form and the Adverse Event CRF. All liver transplantations will be captured as SAEs.

9.5.4.4 Expedited Reporting

The sponsor must inform investigators and regulatory authorities of reportable events, in compliance with applicable regulatory requirements, on an expedited basis (ie, within specific

time frames). For this reason, it is imperative that sites provide complete SAE information in the manner described above.

9.5.4.5 Breaking the Blind

In the case of a medical emergency where the appropriate treatment of the subject requires knowledge of the study treatment given, the investigator may break the randomization code for an individual subject. In all such cases, the AE necessitating the emergency blind break will be handled as an SAE in accordance with the procedures indicated above. Any broken code will be clearly justified and documented. The medical monitor must be notified immediately of the blind break.

9.5.4.6 Regulatory Reporting of Adverse Events

Adverse events will be reported by the sponsor or a third party acting on behalf of the sponsor to regulatory authorities in compliance with local and regional law and established guidance. The format of these reports will be dictated by the local and regional requirements.

All studies that are conducted within any European country will comply with European Good Clinical Practice Directive 2005/28/EC and Clinical Trial Directive 2001/20/EC. All suspected unexpected serious adverse reactions will be reported, as required, to the CAs of all involved European member states.

9.5.5 Completion/Discontinuation of Subjects

A subject may elect to discontinue the study at any time for any reason. All subjects who discontinue the study are to complete the study's early discontinuation procedures the Visit 4 (Procedure Day) assessments for the study will be performed as an end of study visit.

The investigator will promptly explain to the subject involved that the study will be discontinued for that subject and provide appropriate medical treatment and other necessary measures for the subject. A subject who has ceased to return for visits will be followed up by mail, phone, or other means to gather information such as the reason for failure to return, the status of treatment compliance, the presence or absence of AEs, and clinical courses of signs and symptoms. This information will be recorded in the CRF.

Subjects who discontinue early from the study will be discontinued for 1 of these primary reasons: AE(s), lost to follow-up, subject choice, inadequate therapeutic effect, withdrawal of consent, pregnancy, study terminated by sponsor, or administrative/other. In addition to the primary reason, the subject may indicate 1 or more of secondary reasons for discontinuation. Study disposition information will be collected on the Subject Disposition CRF.

A subject removed from the study for any reason may not be replaced.

9.5.6 Abuse or Diversion of Study Drug

Not applicable

9.5.7 Confirmation of Medical Care by Another Physician

The investigator will instruct subjects to inform site personnel when they are planning to receive medical care by another physician. At each visit, the investigator will ask the subject whether he/she has received medical care by another physician since the last visit or is planning to do so in the future. When the subject is going to receive medical care by another physician, the investigator, with the consent of the subject, will inform the other physician that the subject is participating in the clinical study.

9.6 DATA QUALITY ASSURANCE

This study will be organized, performed, and reported in compliance with the protocol, SOPs, working practice documents, and applicable regulations and guidelines. Site audits will be made periodically by the sponsor's or the CRO's qualified compliance auditing team, which is an independent function from the study team responsible for conduct of the study.

9.6.1 Data Collection

Data required by the protocol will be collected on the CRFs and entered into a validated data management system that is compliant with all regulatory requirements. As defined by ICH guidelines, the CRF is a printed, optical, or electronic document designed to record all of the protocol-required information to be reported to the sponsor on each study subject.

Data collection on the CRF must follow the instructions described in the CRF Completion Guidelines. The investigator has ultimate responsibility for the collection and reporting of all clinical data entered on the CRF. The investigator must sign the completed CRF to attest to its accuracy, authenticity, and completeness.

Completed, original CRFs are the sole property of Eisai and should not be made available in any form to third parties without written permission from Eisai, except for authorized representatives of Eisai or appropriate regulatory authorities.

9.6.2 Clinical Data Management

All software applications used in the collection of data will be properly validated following standard computer system validation that is compliant with all regulatory requirements. All data, both CRF and external data (eg, laboratory data), will be entered into a clinical system.

9.7 STATISTICAL METHODS

All statistical analyses will be performed by the sponsor or designee after the study is completed and the database is locked and released for unblinding. However, unblinded safety analyses for review by a DSMB will be conducted by an independent statistical group prior to database lock. Statistical analyses will be performed using SAS[®] software or other validated statistical software

as required. Details of the planned statistical analyses are outlined below; further details will be included in a separate statistical analysis plan (SAP).

9.7.1 Statistical and Analytical Plans

The statistical analyses of study data are described in this section. Further details of the analytical plan will be provided in the SAP, which will be finalized before the unblinded interim safety analyses, final database lock and treatment unblinding, and will be included in the clinical study report. An interim statistical analysis plan, describing the safety analyses planned for the purposes of review by the DSMB, will also be produced.

9.7.1.1 Study Endpoints

PRIMARY ENDPOINTS

The primary efficacy endpoint is the proportion of subjects who do not require a platelet transfusion or any rescue procedure for bleeding after randomization and up to 7 days following an elective procedure.

SECONDARY ENDPOINTS

The secondary efficacy endpoints are:

- Proportion of responders defined as subjects who achieve platelet counts of $\geq 50 \times 10^9/L$ on Procedure Day (ie, prior to receiving a platelet transfusion or undergoing the elective procedure)
- Change from baseline in platelet count on Procedure Day (ie, prior to receiving a platelet transfusion or undergoing the elective procedure)

(revised per Amendment 04)

EXPLORATORY ENDPOINTS

The exploratory endpoints are:

- Platelet count and change from baseline in platelet count at each visit
- Proportion of subjects who achieve platelet count of $\geq 50 \times 10^9/L$, $\geq 75 \times 10^9/L$, or $\geq 200 \times 10^9/L$ at each visit
- Number of platelet units used per platelet transfusion episode
- Severity of bleeding events assessed by WHO bleeding score and BARC bleeding scale
- Proportion of subjects with a WHO bleeding score ≥ 2 after randomization and up to 7 days following an elective procedure (revised per Amendment 04)
- Health economics assessed by resource use

9.7.1.2 Definitions of Analysis Sets

Full Analysis Set (FAS): The FAS is the group of randomized subjects. The FAS will be analyzed “as randomized”.

Per Protocol Set (PP): The PP Set is the group of all randomized subjects who receive protocol-assigned study drug and do not meet any of the following criteria:

- Subjects who have any major protocol violations (major inclusion/exclusion violations or other major protocol violations that impact the evaluation of efficacy)
- Subjects who use a prohibited concomitant medication that affects the assessment of study endpoints
- Subjects who are noncompliant in terms of study medication

A comprehensive list of subjects to be excluded from the PP will be agreed upon by the study team prior to database lock. The PP will be analyzed “as randomized”.

Safety Analysis Set: The Safety Analysis Set is the group of subjects who receive at least 1 dose of study drug and have at least 1 postdose safety assessment. This set will be analyzed “as treated.”

PK Analysis Set: The PK Analysis Set is the group of randomized subjects who receive at least 1 dose of avatrombopag and have at least 1 quantifiable avatrombopag concentration with a documented dosing history.

PK/PD Analysis Set: The PK/PD Analysis Set is the group of randomized subjects who receive at least 1 dose of avatrombopag, have at least 1 quantifiable avatrombopag concentration, and at least 1 platelet count, with a documented dosing history.

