Study E5501-G000-202 evaluated the efficacy, safety, and population PK of once-daily oral avatrombopag dosing, in subjects with chronic liver diseases and thrombocytopenia prior to elective surgical or diagnostic procedures. The primary efficacy endpoint was the proportion of responders with platelet count increases from baseline of $\geq 20 \times 10^9/L$ and a platelet count of $\geq 50 \times 10^9/L$ once from Day 4 through Day 8. The proportion of responders for all avatrombopag-treated subjects was 48.4% compared with 8.1% in the combined placebo group ($P < 0.0001$). All doses of avatrombopag achieved a significantly higher proportion of responders compared with their respective cohort placebo arms and the highest platelet count responses were observed between Days 10 to 14 after first dose. In addition, avatrombopag appeared well tolerated in this patient population. There was no clear trend regarding the incidences of AEs between placebo and avatrombopag treatment groups, and the commonly reported treatment-emergent adverse events (TEAEs) and serious TEAEs were consistent with the disease state of the patient population. The findings from Study E5501-G000-202 suggest that avatrombopag would be an effective therapy for the treatment of thrombocytopenia in patients with chronic liver disease, prior to an elective procedure.

For more detailed information regarding effects in humans, please refer to the Investigator Brochure.

7.1.2.4 Common Serious Adverse Events Expected to Occur in the Study Population Even in the Absence of Study Drug Exposure

Thrombotic/thromboembolic complications may occur in patients with chronic liver disease. Portal vein thrombosis (PVT) is of particular concern in chronic liver disease patients who are prone this type of thrombosis and is often associated with poor portal vein flow. The presence of thrombocytopenia can increase the potential for bleeding, which results in an elevated morbidity and mortality risk in patients with liver disease. In cirrhotic patients undergoing abdominal surgery, bleeding accounts for up to 60% of all causes of death. Thrombocytopenic patients often require multiple platelet transfusions, which can be associated with complications such as systemic infections, iron overload, and platelet refractoriness.⁴

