8.3 EXPLORATORY OBJECTIVES

The exploratory objectives of the study are:

- To characterize the pharmacokinetics and the relationship between avatrombopag plasma concentrations and platelet count using the population approach
- To characterize platelet count changes from baseline, the extent of platelet transfusion use, evaluate the incidence of bleeding events, and assess the severity of any bleeding events (revised per Amendment 04)
- To assess the health economic impact associated with minimizing the need for platelet transfusions and any rescue procedure for bleeding associated with an elective procedure

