9.1.1.1 Screening Period (Visit 1)

Screening will occur between Day -14 and Day -1.

The purpose of the Screening Period is to obtain informed consent and to establish protocol eligibility. Subjects must have a diagnosis of thrombocytopenia associated with liver disease and be scheduled to undergo an elective procedure. Only subjects who, in the opinion of the investigator, are expected to require platelet transfusion to address a risk of bleeding associated with the procedure will be recruited into this study.

Informed consent will be obtained after the study has been fully explained to each subject and before the conduct of any screening procedures or assessments. Procedures to be followed when obtaining informed consent are detailed in [Section 5.3](#).

After providing informed consent, all subjects will undergo screening assessments to ensure that they meet all of the inclusion and none of the exclusion criteria, as described in [Section 9.3.1](#) and [Section 9.3.2](#). Screening assessments and timing are shown in [Section 9.5.2.1 \(Table 5\)](#).

During this phase, the type and schedule of the elective procedure will be confirmed.

The Screening Disposition case report form (CRF) page must be completed to indicate whether the subject is eligible to participate in the study and to provide reasons for screen failure, if applicable.

Rescreen of subjects will only be allowed under the following circumstances:

- Scheduled procedure is cancelled or delayed
- Platelet count inclusion criteria is not met as platelet count tends to fluctuate
- Unable to complete the Screening Period due to administrative, logistical issues
- Previously screen failed due to criteria no longer in the protocol (added per Amendment 01)

Repeat of screening laboratory evaluations are allowed in cases where abnormal result(s) are noted during the Screening Period that are believed to be related to a potential laboratory error or a transient and/or reversible condition (eg, clumped platelets or hemolyzed sample for complete blood count). Results of the repeated assessment must be available before randomization. If additional blood samples are sent to the central laboratory during the Screening Period, eligibility must be assessed based on the most recent laboratory values. The 2 most recent values will be used to determine the mean platelet count value for entry criteria and for assignment to the low or high baseline platelet count cohort.

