9.7.1.7 Pharmacokinetic, Pharmacodynamic, and Pharmacogenomic/Pharmacogenetic Analyses

PHARMACOKINETIC ANALYSES

Plasma concentration versus time data will be listed. The data will be analyzed using a population PK approach to estimate population PK parameters and the effect of covariates on the PK parameters will be evaluated.

For the population PK analysis, data from this study will be pooled with PK data from two Phase 2 studies in subjects with thrombocytopenia associated with liver disease, including hepatitis C, and possibly with data from Phase 1 studies.

The population PK analysis will be performed to characterize the PK of avatrombopag in subjects with thrombocytopenia associated with liver disease, and to screen for potential covariates with any significant and clinically relevant effects on avatrombopag PK. The PK model will be parameterized for absorption rate constant, apparent clearance, and apparent volume of distribution. Derived exposure parameters will be area under the concentration-time curve and maximum plasma concentration.

PHARMACOKINETIC/PHARMACODYNAMIC ANALYSES

The relationship between avatrombopag concentration and platelet count will be analyzed using a population PK/PD approach to estimate population PD parameters and the effect of covariates on the PD parameters will be evaluated.

For the PK/PD modeling, data from this study will be pooled with PK/PD data from two Phase 2 studies in subjects with thrombocytopenia associated with liver disease, including hepatitis C, and possibly with data from Phase 1 studies.

The population PK and PK/PD analyses will be detailed in a separate analysis plan.

PHARMACOGENOMIC/PHARMACOGENETIC ANALYSES

Not applicable

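### The PK/PD Analysis Set leaves out the randomised placebo subjects, so this study's part of the concentration-platelet model has no observed zero-exposure group; adding them is a free improvement

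*Protocol*

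**What the plan says.** Protocol 9.7.1.2 defines the PK/PD Analysis Set as randomised subjects "who receive at least 1 dose of avatrombopag, have at least 1 quantifiable avatrombopag concentration, and at least 1 platelet count". Their dosing history must also be documented. The synopsis repeats this. SAP 5.2.1 does not list a PK/PD set.

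The set serves an exploratory objective in Protocol 8.3: "To characterize the pharmacokinetics and the relationship between avatrombopag plasma concentrations and platelet count using the population approach". Protocol 9.7.1.7 gives the method for that relationship: "analyzed using a population PK/PD approach to estimate population PD parameters and the effect of covariates on the PD parameters will be evaluated". It adds that "data from this study will be pooled with PK/PD data from two Phase 2 studies in subjects with thrombocytopenia associated with liver disease", possibly with Phase 1 data as well. It does not say whether placebo records from those studies enter.

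The model itself is deferred: "The population PK and PK/PD analyses will be detailed in a separate analysis plan". SAP 5.5 also defers it, to one or more plans due before database lock.

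Three other parts of the protocol bear on platelet change without drug:
- Phase 2 result (7.1.2.3): "The proportion of responders for all avatrombopag-treated subjects was 48.4% compared with 8.1% in the combined placebo group". A responder there had a rise of at least 20 and a count of at least 50 (×10^9/L), once between Days 4 and 8.
- Entry (9.3.1): the mean of two counts must be below 50, with neither above 60. Rescreening (9.1.1.1) is allowed when "Platelet count inclusion criteria is not met as platelet count tends to fluctuate".
- Dose (9.1.2.1): 60 mg is given only below 40, and 40 mg only from 40 to below 50. Each cohort has its own randomised placebo group.

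**The concern.** A concentration-platelet model has to separate the rise caused by drug from the change that would have happened anyway. Subjects enter because their counts are low, and counts fluctuate, so some average rise without drug is to be expected. The direct evidence on that rise in this study is the platelet series of randomised subjects with no exposure. A quantifiable avatrombopag concentration is a sensible condition for a PK set. As a condition for the PK/PD set it removes exactly those subjects.

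The dosing rule adds to this. Because dose and baseline cohort coincide, any non-drug rise that differs between cohorts also differs with dose. A drug-only analysis must infer the zero-exposure level in each cohort from the spread of exposures at a single dose. At stake is the accuracy or precision of an exploratory exposure-response estimate. The trial's efficacy conclusions are not at stake.

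**Working it through.** The documents give no figure for the PK/PD analysis, so there is none to reproduce. The check covers how many subjects are excluded, whether selection can produce a non-drug rise, and what the exclusion does to an exposure-response slope.

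**1. Subjects excluded.** Protocol 9.7.2 plans 200 subjects randomised 2:1. 200 × 2/3 = 133.3 and 200 × 1/3 = 66.7, which agree with the stated 133 and 67. The set omits 67/200 = 33.5%.

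**2. Non-drug rise from the entry rule.** The entry rule (both counts at most 60, mean below 50) was simulated with one later count and no drug effect. Assumed, because the documents do not give them: true counts with mean 50–70 and SD 15–30, and within-subject SD 5–11. Over 27 settings the expected rise was about 0.5–7.7 ×10^9/L in the lower cohort and 0.1–5.2 in the higher cohort. It was larger in the lower cohort, which gets the higher dose, in all 27.

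**3. Effect on the slope, one common rise.** Assumed: drug effect 30 ×10^9/L at mean exposure, exposure x scaled to mean 1, log-exposure SD 0.5, residual SD 25, one count per subject, 133 treated and 67 placebo. With treated subjects only and no non-drug term, the bias is g·E[x]/E[x²] = g/e^0.25 = g/1.284 for a rise g. Simulation agrees:

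| Non-drug rise g | 30 + g/1.284 | Simulated, no non-drug term |
|---|---|---|
| 0 | 30.0 | 30.0 |
| 3 | 32.3 | 32.4 |
| 5 | 33.9 | 34.0 |
| 10 | 37.8 | 37.8 |

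With a non-drug term, the simulated estimate is 29.9 to 30.1 for every g, whether or not placebo subjects are included.

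**4. Effect on the slope, rise differing by cohort.** Take g = 4.1 (lower) and 1.9 (higher), both inside the ranges in step 2. There are 67 treated and 33 placebo subjects per cohort. Exposure is taken as proportional to dose, 60/40 = 1.5, so mean x is 1.2 and 0.8.
- E[xg] = ½(1.2×4.1 + 0.8×1.9) = 3.22
- E[x²] = 1.284 × ½(1.44 + 0.64) = 1.335
- No non-drug term: bias 3.22/1.335 = 2.4, estimate 32.4.
- One common term: bias (3.22 − 1×3.0)/(1.335 − 1) = 0.66, estimate about 30.7.
- Cohort-specific terms: no bias, with or without placebo.

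Precision with cohort-specific terms is SE = 25/√SS, where SS is the within-cohort sum of squares of x.
- Treated only: SS = 67 × 0.284 × (1.44 + 0.64) = 39.6, so SE = 4.0 (simulated 4.1).
- Placebo added at x = 0: SS = (123.9 − 80.4²/100) + (55.1 − 53.6²/100) = 59.2 + 26.3 = 85.6 before rounding, so SE = 2.7 (simulated 2.7).

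The simulated ratio is 4.1/2.7 = 1.5, or about 2.3 times the variance.

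**The case against.** The strongest reply is that neither document gives the structure of the PD model. A reader might infer from the set definition that non-drug rises are bound to be attributed to avatrombopag. That does not follow. The separate plan may contain a suitable non-drug term, and step 3 shows that a treated-only fit with the right term is unbiased. Placebo records may also enter through pooling, since the Phase 2 liver-disease study had placebo arms. This reply stands against any claim of certain bias. It does not answer the loss of precision in this study's contribution, and a single common term may leave a small bias when drift differs by cohort.

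Three other strong readings also fail.
- Placebo subjects are not the only information on drift. Treated subjects have two pre-dose counts and a count about 30 days after the last dose, and individual exposures vary.
- Dividing 8.1% by 48.4% gives a ratio of responder rates for a threshold reached once. It is neither a mean drift nor a misattributed share of the effect.
- The protocol does not say that this study's model will select a dose. Sections 7.2 and 9.4.4 say that the Phase 3 doses had already been chosen from modelling of Phase 2 data.

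It is also true that the platelet effect is tested against randomised placebo in SAP 5.4.2.1, 5.4.2.2 and 5.4.3.1, which do not use this set.

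**Conclusion.** The exclusion is certain: it follows from the definition and removes about 67 of 200 randomised subjects. The consequence is conditional. If the unseen model has no adequate non-drug term and no placebo data come in through pooling, part of the non-drug rise may enter the drug effect: 32.4 against a true 30 in the cohort-specific illustration, or about 30.7 with one common term. If the model has cohort-specific terms, the cost is precision, with a standard error of about 4.1 instead of 2.7.

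These sizes rest on assumed values for drug effect, residual SD, exposure spread, drift and dose-proportional exposure, and on a linear model with one count per subject. They show direction and rough scale and do not predict this study's results. The ratio of standard errors depends on the assumed exposure spread, and pooled placebo data would reduce the gain.

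Severity is low, because the analysis is exploratory and the randomised efficacy analyses are unaffected.

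**What to change.** In Protocol 9.7.1.2 and the synopsis, widen the PK/PD Analysis Set to add randomised placebo subjects who have documented dosing and one or more platelet counts, entered at zero concentration. Leave the PK Analysis Set as it is.

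Before database lock, have the separate PK/PD plan:
- include a non-drug platelet-change term that can differ by baseline cohort;
- state whether placebo records from the pooled studies are used;
- state how counts taken after a platelet transfusion are handled in both groups.

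The cost is a change to one definition and a few lines in the PK/PD plan, which may already hold some of them. Placebo platelet counts are already scheduled (Protocol Table 5), so there are no new samples or visits, and there is no effect on the trial's Type I error.
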